### 8.3. Investigational Drug Manufacturing, Packaging and Labeling

Investigational drug used in this study will be prepared, packaged, and labeled in accordance with the standard operating procedures (SOPs), Good Manufacturing Practice (GMP) guidelines, International

Avalyn Pharma, Inc.  
AP01-002

Protocol V2.1  
12 OCT2020

Conference on Harmonization (ICH) guidelines for Good Clinical Practice (GCP), guidelines for Quality System Regulations (QSR), and applicable regulations.

### 8.3.1. Drug Substance

The manufacturer of cGMP pirfenidone drug substance for this study is Procos S.p.A, Italy.

### 8.3.2. Drug Product

AP01 is a sterile, aqueous solution formulation consisting of pirfenidone (active ingredient) dissolved in a 5 mM citrate buffer containing sodium chloride (for osmolality and tolerability improvement) and sodium saccharin (to improve taste and tolerability). AP01 is formulated with an osmolality ~380 milliosmoles/kg with a final pH ~6.0. All excipients have good history of use in pharmaceutical products and have been used in United States Food and Drug Administration (US FDA), European and Australian-approved inhalation solutions. AP01 IP has been tested in a Phase 1 study with the composition presented in Table 8. All excipients have good history of use in pharmaceutical products and have been used in US FDA, European and Australian-approved inhalation solutions.

**Table 8: Drug Product Composition**

Ingredient	Function	Concentration
Pirfenidone	Active pharmaceutical ingredient	12.5 mg/mL
Sodium citrate dihydrate	Buffering agent	4.5 mM
Citric acid monohydrate	Buffering agent	0.5 mM
NaCl	Osmolality adjustment/Tolerability improvement	150 mM
Sodium saccharin dihydrate	Taste/Tolerability improvement	0.75 mM
Sterile Water for Injection	Vehicle	q.s.

### 8.3.3. Manufacture of Drug Product

AP01 IP is manufactured by Holopack GmbH in Sulzbach-Laufen, Germany. The manufacturing process is comprised of formulation compounding, aseptic filling into low density polyethylene (LDPE) ampoules by the blow-fill-seal (BFS) operation, and secondary packaging filled ampoules in foil laminate overwrap. Release and stability testing is conducted at Pharmaceutical Product Development, Inc., located in Middleton, Wisconsin, United States of America.

### 8.3.4. Nebulization Device

The nebulizer is a re-usable device intended for single patient use. AP01 will be delivered to the lung by oral inhalation using the PARI (Germany) eFlow® Nebulizer System. The eFlow is a high-efficiency, 510(k)-cleared, Conformité Européenne (CE)-marked device that is marketed with other products for other disease indications.

With the AP01 formulation, the eFlow nebulizer (model with large holding chamber and with 35 membrane head) produces an aerosol with a narrow particle size distribution with a mass median diameter of 2.9 – 3.9 µm and a GSD < 1.8, which is well suited to lower airway and alveolar drug deposition.

Avalyn Pharma, Inc.  
AP01-002

Protocol V2.1  
12 OCT2020

### **8.3.5. Packaging and Labeling of AP01 and Nebulizer Kits**

#### AP01 IP Supply

Overwrapped AP01 IP ampoules will be packaged and labelled as required by regional regulation by PPD Development, L.P. in Athlone, Ireland. Each IP carton will contain 18 AP01 overwrapped pouches, each pouch containing two ampoules. Each ampoule will contain 4 mL AP01 12.5 mg/mL formulation, which is a 50 mg dose. The 50 mg once daily inhaled dose cohort will use one IP carton every 4 weeks (1/2 pouch per day; 1 ampoule per once daily dose). The 100 mg twice daily inhaled dose cohort will use four IP cartons every 4 weeks (2 pouches per day; 2 ampoules per twice daily dose). Details of IP distribution will be outlined in the clinical study manual.

#### Nebulizer Starter Kits and Replacement Handsets

Randomized patients will receive an eFlow nebulizer starter kit with their initial AP01 IP cartons at the Baseline visit. At subsequent visits, patients will receive an eFlow replacement handset to exchange with their used handset every 4 weeks or as needed. Nebulizer starter kits will be packaged separately from IP cartons. Nebulizer starter kits will comprise of a single box with a study-specific label as required by regional regulation. Replacement handsets will be packaged separately from eFlow starter kits and IP cartons. Each eFlow replacement handset will be packaged with a study-specific label as required by regional regulation. Details of device distribution will be outlined in the clinical study manual.

### **8.4. Investigational Drug and Device Storage**

Manufactured IP and nebulizer supplies must be kept in a secure, limited access storage area maintained under room temperature (15° - 25° Celsius).

### **8.5. Investigational Drug Preparation**

The IP is to be kept in the aluminum foil pouch until the point of use.

The patient should be instructed not to use this IP with any other nebulizers, and not to use this eFlow with any other drug products. Details regarding drug preparation will be outlined in the clinical study manual.

### **8.6. Investigational Drug Administration**

Patients will be trained on use of the eFlow and administration of the study drug at the Baseline visit. The first dose of study drug for each patient will be administered and observed at the clinical study site at the Baseline visit to confirm tolerability. All subsequent doses will be administered by the patient at home. All doses must be taken at least 4 hours apart.

Patients who experience cough that limits their ability to complete dosing will be given 1 – 2 puffs (90 - 100 µg) of an inhaled beta 2 agonist, such as salbutamol, in order to complete the in-clinic dose. These patients, as well as patients with a history of asthma or smoking history of 20 pack years or greater, or patients that have a  $\geq 15\%$  drop in FEV1 percent predicted in their pre-dose and post-dose readings and are symptomatic will be provided with and required to use 1 - 2 puffs (90 - 100 µg) of salbutamol prior to their second dose and for dosing throughout the study, unless these patients are currently taking a long-

Avalyn Pharma, Inc.  
AP01-002

Protocol V2.1  
12 OCT2020

acting beta-2-agonist therapy. If symptoms persist with study treatment despite beta-2-agonist therapy, the Investigator will assess and discontinue the patient due to tolerability issues if he/she deems it necessary.

## **8.7. Missed Doses and Dose Modifications**

Doses that are missed can be taken in a 24-hour period, as long as doses are 4 hours apart.

In the event of excessive coughing while drug administration at home, the patient will contact the site to determine how to proceed. Salbutamol may be prescribed to be administered prior to dosing, as described in section 8.6, if deemed necessary by the investigator.

If AP01 is stopped during treatment due to intolerance, restart dosing when the patient has improved. The initial dose after restarting should be observed for tolerance.

It is recommended to reduce the 100 mg twice daily dose to 50 mg twice daily if the patient cannot tolerate the 100 mg dose. If the 50 mg twice daily dose cannot be tolerated, the patient may have their dose reduced to 50 mg once daily.

## **8.8. Investigational Drug Accountability, Handling and Disposal**

### **8.8.1. Investigational Drug Handling and Disposal**

Administration of the first dose of IP will be observed by the investigator or designee; time of administration and confirmation of full dose being administered will be noted on the eCRFs.

The investigator or designee is responsible for IP and accountability, reconciliation and record maintenance. In accordance with all applicable regulatory requirements, designated research or pharmacy staff at each study site must maintain IP accountability records for study drug throughout the course of the study.

Patients will be instructed to bring back the box(es) of unused ampoules at each study visit for drug accountability purposes. Patients will be instructed to dispose of all used ampoules. Details regarding drug accountability procedures will be captured in the clinical study manual.

### **8.8.2. Salbutamol Handling and Disposal**

Patients requiring salbutamol as described in Sections 8.6 and 8.7 will be provided with salbutamol at the study visits or as needed. Patients will dispose of the salbutamol at the end of the study.

### **8.8.3. Device Handling, Cleaning and Disposal**

The eFlow instructions for use provide detailed instructions for the patient to follow regarding cleaning and maintenance of the handsets for this study.

In the event of a nebulizer (base unit, handset or both) malfunction, the patient will contact the site immediately for a replacement unit. The patient will return the malfunctioning nebulizer to the site. The site will return the malfunctioning nebulizer to the manufacturer (via the clinical packager) for a root cause analysis. Further details regarding the handling of malfunctioning devices will be outline in the clinical study manual.

Avalyn Pharma, Inc.  
AP01-002

Protocol V2.1  
12 OCT2020

In accordance with all applicable regulatory requirements, designated research or pharmacy staff at each study site must maintain accountability records for the nebulizer system (base units and handsets) throughout the course of the study. Details regarding device accountability procedures will be captured in the clinical study manual.

## **8.9. Treatment of Patients**

### **8.9.1. Concomitant Medications and/or Treatments**

Patients are prohibited from receiving pirfenidone or nintedanib within 3 days prior to randomization to the study and during participation in Part A of the study. Other than brief periods of medically appropriate treatment for acute IPF exacerbation, patients will not receive any other therapy for the treatment of IPF in Part A of the study. If in the opinion of the investigator, a patient is in need of treatment with oral pirfenidone or nintedanib during Part A, the patient should be discontinued from the study and return to the clinic for their Early Termination visit. Nintedanib, but not oral pirfenidone, use is allowed if deemed necessary by the investigator during Part B of the study. If AP01 is stopped during treatment of an exacerbation due to a patient's intolerance, it should be restarted when the patient has improved, however the first dose should be observed for tolerance. Oxygen use is allowed during the study.

Due to the low systemic levels expected with delivery by inhalation, drug-drug interactions are unlikely and unexpected.

Patients who are experience excessive coughing during study drug administration will be required to inhale 1 - 2 puffs (90 - 100 µg) of salbutamol within 10 minutes prior to subsequent study drug dosing. Pre-treatment with salbutamol will be documented on the Concomitant Medications eCRF page.

### **8.9.2. Treatment Compliance**

Administration of the first dose of IP will be observed by the investigator or designee; time of administration and confirmation of full dose being administered will be noted in the eCRF. Patients will bring all unused ampoules to each visit for drug accountability and compliance assessment. At the discretion of the investigator, patients that are not in compliance with study dosing and procedures will be discontinued from the study.

Avalyn Pharma, Inc.  
AP01-002

Protocol V2.1  
12 OCT2020

## **9 RANDOMIZATION AND BLINDING PROCEDURES**

### **9.1 Randomization**

Patients will be randomized in a 1:1 ratio to receive AP01 either 50 mg once daily or 100 mg twice daily; both regimens being administered by the eFlow. The randomization schema will be stratified by region (Asia-Pacific and Europe) and by disease severity (FVC < 50% predicted and FVC ≥ 50% predicted). The first 20 patients randomized in the study must have FVC ≥ 50% predicted at Screening. After the first 20 patients have been randomized, patients with FVC 40% < 50% predicted will be allowed to be randomized in the study but randomization for these patients will be capped at 20.

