12 OCT 2020

The initial dose of drug will be administered in the clinic to confirm airway tolerance. If based on the investigator's opinion, the patient had tolerability issues during the first dose administration, a second dose, at least 4 hours later, will also be observed. Patients who experience cough that limits their ability to complete dosing will be given 1 - 2 puffs (90 - 100 micrograms ( $\mu\text{g}$ )) of salbutamol in order to complete the in-clinic dose. These patients, as well as patients with a history of asthma or smoking history of 20 pack years or greater, or patients that have a  $\geq 15\%$  drop in FEV1 percent predicted in their pre-dose and post-dose readings will be required to use 1 - 2 puffs (90 - 100  $\mu\text{g}$ ) of salbutamol prior to dosing throughout the study unless these patients are currently taking a long-acting beta-2-agonist therapy.

Patients will have a telephone assessment at Week 1 and in-clinic assessments at Weeks 4, 8, 12, 16, 20, and 24. The Data and Safety Monitoring Board (DSMB) will perform a review of safety data from the first 20 patients after Week 4 to confirm the safety and airway tolerability of multiple dose administration. A decision to stop, continue or modify the study will be made based on this review.

Part B will collect long term safety and efficacy data for an additional 48 weeks. Patients who complete Part A through Week 24 and, in the opinion of the investigator are compliant with treatment, may select to continue the treatment to which they were randomized. The DSMB for this study met on 12 OCT 2020 to review preliminary dose comparison data. It was determined that the 100 mg twice daily dose showed a trend for amelioration of FVC loss and recommended all patients in Part B be treated with the 100 mg twice daily dose. Therefore, all patients who participate in Part B after the implementation of this amendment will be treated with the 100 mg twice daily dose. Patients participating in the AP01-005 study will continue treatment that they are receiving at Visit 12 on this study and then transition to the Rollover study upon approval of AP01-005 at their site.

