12 OCT 2020

## 5.7. Stopping Rules

This study may be discontinued at any time if, in the opinion of the DSMB, investigator, or Avalyn Pharma, continuation of the study represents a significant medical risk to participating patients. The DSMB will perform a safety data review after 20 patients have completed Week 4 and will make a recommendation at that time as to whether the study should continue or be modified. Avalyn Pharma also reserves the right to terminate the study at any time for any reason.

Avalyn Pharma, Inc.  
AP01-002

Protocol v2.1  

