### **15.3 Data and Safety Monitoring Board**

An independent DSMB will review accumulated individual safety data for the first 20 patients after their first four weeks of treatment. The data to be reviewed will be unblinded since this is an open-label study. Based on this review, the DSMB will make a recommendation to continue, modify or stop the study. Enrollment will continue during the DSMB review unless 5 or more of the first 20 patients are discontinued due to intolerance.

At any time during the study, should any untoward safety issue be observed, the DSMB Chair may schedule an immediate meeting to review the relevant safety data.

Avalyn Pharma, Inc.  
AP01-002

Protocol V2.1  

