6.6. Subgroups

Subgroup analyses will be performed based on baseline groupings for FVC % predicted (FVC % predicted \leq 65, 65 < FVC % predicted < 80, and FVC % predicted \geq 80 at Baseline), region (Asia-Pacific and Europe), supplemental oxygen use (Y/N), age at screening categorized as >Median level vs. \leq Median level, sex, DLCO % predicted categorized as >Median level vs. \leq Median level, and progression-related biomarkers (CXCL13, CCL18, MMP3) each categorized as >Median level vs. \leq Median level provided each stratum contains at least 10 patients. Analyses of the primary efficacy endpoint will be performed by each subgroup in addition to by treatment group. In addition, a general

This document is confidential.

SAP Version: 3.0 (15JUL2021)
Controlled Document ID: **3903A.01**, Effective Date 29-Oct-2018
Filing requirements: TMF

Page 24 of 52

Statistical Analysis PlanSponsor: Avalyn Pharma, Inc.; Protocol No.: AP01-002

safety summary (overall AE summary, summary of respiratory [SOC respiratory, thoracic and mediastinal disorders] TEAEs by Preferred Term and summary of tolerability including cough due to drug administration and bronchospasm after in-clinic drug administration) will be performed by each subgroup in addition to by treatment group.

This document is confidential.

SAP Version: 3.0 (15JUL2021)
Controlled Document ID: **3903A.01**, Effective Date 29-Oct-2018
Filing requirements: TMF

Page 25 of 52

Statistical Analysis PlanSponsor: Avalyn Pharma, Inc.; Protocol No.: AP01-002

7. Demographic, Other Baseline Characteristics and Medication**7.1. Patient Disposition and Withdrawals**

The number of patients in each study population will be summarized by treatment group and overall. In addition, for each study part (Part A and Part B), patients' status with regard to study treatment and follow-up will also be summarized by treatment group and overall, along with the reasons for study discontinuations. The timing of the switch to 100 mg twice daily in Part B for 50 mg once daily patients and duration of time on 100 mg twice daily will be summarized.

All patient disposition data will be presented in a listing.

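### No planned safety summary separates the FVC 40 to <50% stratum, which the protocol restricts and caps, from patients with FVC 50 to 65%

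*Protocol*

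**What the plan says.** Protocol 9.1, repeated in SAP 3.6, gives the lower-FVC patients three special rules.

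- **Hold-back:** "The first 20 patients randomized in the study must have FVC ≥ 50% predicted at Screening". The group opens on a count: "After the first 20 patients have been randomized, patients with FVC 40% < 50% predicted will be allowed to be randomized".
- **Cap:** "randomization for these patients will be capped at 20".
- **Stratum:** randomisation is stratified by region and "by disease severity (FVC < 50% predicted and FVC ≥ 50% predicted".

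The scheduled DSMB review uses data "from the first 20 patients after Week 4 to confirm the safety and airway tolerability of multiple dose administration" (Protocol 4.1). On timing, Protocol 5.7 says: "The DSMB will perform a safety data review after 20 patients have completed Week 4". Protocol 15.3 adds: "Enrollment will continue during the DSMB review unless 5 or more of the first 20 patients are discontinued due to intolerance". Outside that review the DSMB receives all SAEs as they occur (Protocol 10.1.5.4), and its Chair may call a meeting on a safety issue (15.3).

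Protocol 11.2 asks for subgroups by baseline FVC without giving cut points. SAP 6.6 supplies them, using Baseline values: at or below 65, "65 < FVC % predicted < 80, and FVC % predicted" at or above 80. The same section applies the subgroups to the overall adverse event summary, the respiratory TEAE summary and the tolerability summary (cough on dosing, bronchospasm after in-clinic dosing), and SAP 10.1 refers back to it. The first-dose FEV1 table (SAP 10.6) is by treatment group only. The 50% cut appears in SAP 7.4, as a baseline characteristic.

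**The concern.** Safety and tolerability is the primary objective (Protocol 4.1, SAP 3.1). The protocol marks out one group for restricted entry on the ground of lung function, and the analysis plan then does not report how that group tolerated the drug. In every subgroup table these patients are pooled with those at 50 to 65%. If tolerability is worse below 50%, the pooled row understates it, by an amount that depends on how many patients at 50 to 65% happen to enrol. The scheduled DSMB review cannot fill the gap, because none of its 20 patients comes from this stratum.

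The stake is descriptive. A reader planning a later study would want to know whether the most impaired patients tolerated inhaled dosing, and would have to assemble the answer from listings.

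**Working it through.** **1. Membership.** The first 20 randomised all have Screening FVC ≥50%, and the Week 4 review covers the first 20. Patients with FVC <50% in that review: 0.

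**2. Where the stratum lands in the SAP.** A patient screened at 49.9% leaves the lowest band only with a Baseline value above 65, a relative rise of 65/49.9 − 1 = 30%. Inclusion criterion 8 limits the Screening to Day 1 difference to under 10%. Read as a limit in both directions, it gives at most 49.9 × 1.10 = 54.9. Even if the signed formula is read as limiting falls only, a 30% rise is implausible. In practice the whole stratum falls in the ≤65 row.

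**3. The plan's own detection figure.** Protocol Table 10 uses P(at least one event) = 1 − (1 − p)^n. With n = 50 and p = 1%, 5%, 10% this gives 0.395, 0.923, 0.995, matching the table.

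**4. The same formula for this stratum.** n = 20 is the cap; n = 10 is about one arm under 1:1 stratified randomisation.

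| n | p = 1% | p = 5% | p = 10% |
|---|---|---|---|
| 20 | 0.182 | 0.642 | 0.878 |
| 10 | 0.096 | 0.401 | 0.651 |

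For example, 1 − 0.95^20 = 0.642 and 1 − 0.90^10 = 0.651.

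**5. What zero events would exclude.** The one-sided 95% upper bound is 1 − 0.05^(1/n): 5.8% at n = 50, 13.9% at n = 20, 25.9% at n = 10. The upper limit of a two-sided exact 95% interval is 1 − 0.025^(1/n): 16.8% at n = 20, 30.8% at n = 10.

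**6. How far pooling could hide a difference.** The documents give no event rates by FVC and no expected size for the ≤65 group, so both are assumed. Let M be the size of that group, including 20 patients below 50% with rate r1; the others have rate r2. The displayed rate is (20·r1 + (M − 20)·r2)/M.

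| Assumed r1, r2 | M = 25 | M = 40 | M = 60 |
|---|---|---|---|
| 30%, 10% | 26.0% | 20.0% | 16.7% |
| 20%, 10% | 18.0% | 15.0% | 13.3% |
| 10%, 10% | 10.0% | 10.0% | 10.0% |

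For example, (20 × 0.30 + 40 × 0.10)/60 = 16.7%. The table illustrates the mechanism and predicts nothing. If the rates are equal, nothing is hidden.

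**The case against.** The strongest reply is that these patients are not unobserved. Their first dose is supervised with post-dose spirometry, they are called at Week 1, their SAEs go to the DSMB, they are in every overall safety table and in the ≤65 row, and all their data are listed. All of this stands. It narrows the point to the absence of a separate summary. It does not remove it: cough, a fall in FEV1 or stopping for intolerance need not be serious, and a listing is not a summary.

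A second reply is that the numbers are too small to settle anything. That is right about inference, particularly by arm. But the study plans no formal safety comparison, and a full stratum of 20 exceeds the 10-patient minimum in SAP 6.6.

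A reader might also infer something stronger: that the hold-back fails because release depends on a randomisation count and so comes before the DSMB has seen Week 4 data. The order of events is as described. Week 4 is Day 28 ± 3, so the 20th patient's visit falls on Day 25 at the earliest, whereas the 21st patient may be randomised at once. But no section says the hold-back was meant to await the DSMB. Protocol 15.3 states openly that enrolment continues during the review, subject to the pause at 5 of 20. That pause is a partial brake: with X ~ Binomial(20, p), P(X ≥ 5) is 0.04, 0.37 or 0.76 at a true rate of discontinuation for intolerance of 10%, 20% or 30%. Protocol v2.1 also reports preliminary six-month results (1.2.4) and patients already in Part B (Synopsis), so the release point has evidently passed.

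**Conclusion.** The gap is in reporting. The plan recruits, caps and stratifies on FVC below 50%, then tabulates safety on cut points that merge this stratum with patients at 50 to 65%. It concerns at most 20 of about 100 patients. The documents do not show that the stratum was unmonitored or that the enrolment staging was defective, and neither should be read into this point.

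The added summary would show a common problem and could not exclude a moderate one. The chance of seeing at least one event at a true rate of 5% or 10% is 64% or 88% with 20 patients, and 40% or 65% with about 10 per arm. Zero events would leave one-sided upper bounds of 13.9% and 25.9%. These figures assume that the cap fills and the arms split evenly; with fewer patients, precision is worse. The conclusion about the missing summary rests on the text and on none of the assumed rates.

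**What to change.** **SAP 6.6 and 10.1:** add the randomisation stratum, Screening FVC <50% versus ≥50% predicted, to the subgroups for the overall adverse event summary, the respiratory TEAE summary and the tolerability summary.

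**SAP 10.6:** show the first-dose FEV1 table by the same stratum.

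Present counts and percentages with exact 95% intervals, overall and by arm, without tests. State beside the tables the precision given above. Say how the 10-patient minimum applies to this stratum, since arm-level cells will hold about 10 at most. Because SAP 10.1 refers back to 6.6, and 6.6 also governs the primary efficacy endpoint, say whether the new level applies beyond the tables named here.

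**Cost:** one more subgroup level in existing tables, one more split in the FEV1 table, and a short SAP amendment. The data are already collected.

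No change to the enrolment rule is proposed. At most, the sponsor could be asked to reconcile the count-based release in Protocol 9.1 with the purpose and timing of the Week 4 review in Protocol 4.1, 5.7 and 15.3.
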